| 10-10-10 | 15 | 18 - 40 years | x | x | 1 |
| PLACE1 | 15 | 18 - 40 years | x | x | 1 |
| 10-10-10-AS | 30 | 50 - 70 years | x | x | 2 |
| 10-10-3-AS | 30 | 50 - 70 years | x | x | 2 |
| PLACE2 | 30 | 50 - 70 years | x | x | 2 |

Table 2 Study groups and treatment foreseen in the study

| Treatment name | Vaccine/ product name | Study Groups | | | | |
|----------------------------|-----------------------|--------------|-------------|------------|--------|--------|
| | | 10-10-10 | 10-10-10-AS | 10-10-3-AS | PLACE1 | PLACE2 |
| 10-10-10/Plain | NTHi-Mcat 10-10-10 | x | | | | |
| | NaCl | | | | | |
| 10-10-10/AS01 _E | NTHi-Mcat 10-10-10 | | x | | | |
| | AS01E | | | | | |
| 10-10-3/AS01 _E | NTHi-Mcat 30-30-10 * | | | x | | |
| | AS01E | | | | | |
| Placebo | NaCl | | | | x | x |

* Vials containing 37.5 µg, 37.5 µg and 12.5 µg of freeze-dried PD, PE-PilA and UspA2, respectively, will be diluted in three volumes of AS01_E (total of ~1875 µL). 0.5 mL will be administered.

- **Control:** Placebo control.
- **Vaccination schedules:** 0, 2 months (i.e. at Visit 1 [Day 0] and Visit 4 [Day 60]).
- **Treatment allocation:** Subjects will be allocated to a study group using a centralised randomisation system on internet (SBIR). SBIR will also be used for treatment allocation of the second dose. The randomisation algorithm will use a minimisation procedure accounting for centre at Step 1 and accounting for age (50-59 years or

60-70 years), for smoking status (current or former smokers), for centre and for forced expiratory volume in 1 second (FEV₁) / forced vital capacity (FVC) (≥ 0.7 or < 0.7) at Step 2.

- **Blinding:** Observer-blind.

Table 3 **Blinding of study epochs**

| Study Epochs | Blinding |
|--------------|----------------|
| Epoch 001 | observer-blind |
| Epoch 002 | observer-blind |

- **Sampling schedule:**
 - Blood samples for **safety** (haematology/ biochemistry) will be collected from all subjects at Screening Visit (pre-Day 0), at Visit 1 (Day 0), Visit 2 (Day 7), Visit 4 (Day 60), Visit 5 (Day 67), Visit 7 (Day 210) and at Visit 8 (Day 420).
 - Blood samples for **immunogenicity** will be collected from all subjects for humoral immunity at Visit 1 (Day 0), Visit 3 (Day 30), Visit 4 (Day 60), Visit 6 (Day 90), Visit 7 (Day 210) and at Visit 8 (Day 420), and from a sub-cohort of subjects for cell-mediated immunity (CMI) at Visit 1 (Day 0), Visit 4 (Day 60), Visit 6 (Day 90), Visit 7 (Day 210) and at Visit 8 (Day 420).

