4.3.1. Healthy adults 18-40 years old (Step 1)

The following criteria should be checked at the time of study entry. If ANY exclusion criterion applies, the subject must not be included in the study:

- Use of any investigational or non-registered product (drug or vaccine) other than the study vaccines within 30 days preceding the first dose of study vaccine, or planned use during the study period.

- Concurrently participating in another clinical study, at any time during the study period, in which the subject has been or will be exposed to an investigational or a non-investigational vaccine/product (pharmaceutical product or device).
- Planned administration/ administration of a vaccine not foreseen by the study protocol in the period starting 30 days before the first dose and ending 30 days after the last dose of vaccine, with the exception of any influenza vaccine which may be administered ≥ 15 days preceding or following any study vaccine dose.
- Previous vaccination with any vaccine containing NTHi and/or Mcat antigens.
- Chronic administration (defined as more than 14 days in total) of immunosuppressants or other immune-modifying drugs within 6 months prior to the first vaccine dose. For corticosteroids, this will mean prednisone ≥ 20 mg/day, or equivalent. Only topical steroids are allowed.
- Administration of long-acting immune-modifying drugs at any time during the study period (e.g. infliximab).
- Administration of immunoglobulins and/or any blood products within the 3 months preceding the first dose of study vaccine or planned administration during the study period.
- Any confirmed or suspected immunosuppressive or immunodeficient condition, based on medical history and physical examination (no laboratory testing required).
- History of or current autoimmune disease.
- Laboratory evidence of clinically significant haematological (complete blood cell count [RBC, WBC], WBC differential count [lymphocytes, neutrophils and eosinophils], platelets count or haemoglobin level) and biochemical (alanine aminotransferase [ALT], aspartate aminotransferase [AST] or creatinine) abnormalities as per the opinion of the investigator.
- Acute disease and/or fever at the time of enrolment.
 - Fever is defined as temperature $\geq 37.5^{\circ}\text{C}$ for oral or axillary route. The preferred route for recording temperature in this study will be oral.

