- Laboratory evidence of clinically significant* haematological (complete blood cell count [RBC, WBC], WBC differential count [lymphocytes, neutrophils and eosinophils], platelets count or haemoglobin level) and biochemical (ALT, AST or creatinine) abnormalities.

* As the subjects are adult or elderly, current or former smokers, various pre-existing laboratory abnormalities might be detected. The investigator should use his clinical judgement to decide which ones are clinically significant.

- Acute disease and/or fever at the time of enrolment.
 - Fever is defined as temperature $\geq 37.5^{\circ}\text{C}$ for oral or axillary route. The preferred route for recording temperature will be oral.
 - Subjects with a minor illness (such as mild diarrhoea, mild upper respiratory infection) without fever may be enrolled at the discretion of the investigator.
- Current alcoholism and/or drug abuse.

Please refer to the [glossary of terms](#) for the definition of alcoholism.

- Has significant disease (including significant neurological or psychological disorders), in the opinion of the investigator, likely to interfere with the study and/or likely to cause death within the study duration.
- History of or current condition preventing intramuscular injection as bleeding or coagulation disorder.
- Malignancies within previous 5 years (excluding non-melanoma skin cancer) or lymphoproliferative disorders.
- Pregnant or lactating female.
- Female planning to become pregnant or planning to discontinue contraceptive precautions.
- Any other condition that the investigator judges may interfere with study findings.

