5.7.4.2. Haematology and biochemistry

Table 13 Haematology/ biochemistry

| Blood sampling time point | | Sub-cohort Name | No. subjects | Component |
|--------------------------------|---------------------|-----------------|--------------|--|
| Type of contact and time point | Sampling time point | | | |
| Screening* (Pre-Day 0) | Screening | All subjects | ~120 | Haematology (leukocytes [white blood cells], white blood cell differential count [neutrophils, lymphocytes, eosinophils, basophils, monocytes], erythrocytes [red blood cells], haemoglobin, platelets) |
| Visit 1 (Day 0) | Pre-Vacc I | All subjects | ~120 | |
| Visit 2 (Day 7) | Post-Vacc I | All subjects | ~120 | |
| Visit 4 (Day 60) | Post-Vacc I | All subjects | ~120 | |
| Visit 5 (Day 67) | Post-Vacc II | All subjects | ~120 | |
| Visit 7 (Day 210) | Post-Vacc II | All subjects | ~120 | Biochemistry (ALT, AST, creatinine) |
| Visit 8 (Day 420) | Post-Vacc II | All subjects | ~120 | |

ALT: Alanine aminotransferase; AST: Aspartate aminotransferase

Screening evaluations may be completed 1 to 28 days before Day 0. Site staff should allow sufficient time between the Screening and Day 0 visits to receive and review screening safety laboratory test results. If a delay occurs such that the interval between Screening and the Day 0 vaccination exceeds 28 days, a re-screening visit should be scheduled before Visit 1 during which blood sample collection for safety laboratory assessment should be repeated.

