5. ENDPOINTS

5.1. Primary endpoints

- Occurrence of each solicited local and general AE, during a 7-day follow-up period (i.e. day of vaccination and 6 subsequent days) post-Dose 1 and post-Dose 2, in all subjects, in all vaccine groups.
- Occurrence of any unsolicited AEs, during a 30-day follow-up period (i.e. day of vaccination and 29 subsequent days) post-Dose 1 and post-Dose 2, in all subjects, in all vaccine groups.
- Occurrence of haematological and biochemical laboratory abnormalities, after vaccination, in all subjects, in all vaccine groups:
 - Any haematological (RBC, WBC and differential count, platelets count and haemoglobin level) or biochemical (ALT, AST and creatinine) laboratory abnormality on Day 7, Day 60, Day 67, Day 210 and Day 420.
- Occurrence of any SAE, occurring from first vaccination (Day 0) to study conclusion (Day 420) in all subjects, in all vaccine groups.
- Occurrence of any pIMD occurring from first vaccination (Day 0) to study conclusion (Day 420) in all subjects, in all vaccine groups.

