7.1.2. Analysis of safety

The primary analysis will be performed on the TVC and, if in any vaccine group and at any time point the percentage of vaccinated subjects excluded from the ATP cohort is at least 10%, a second analysis will be performed on the ATP cohort to complement the TVC.

The percentage of subjects with at least one local AE (solicited and unsolicited), with at least one general AE (solicited and unsolicited) and with any AE during the 7-day or 30-day follow-up period will be tabulated after Dose 1 and Dose 2 and overall with exact 95% CI. The same computations will be done for Grade 3 AEs, any AEs causally related to vaccination and any Grade 3 AEs causally related to vaccination.

The percentage of subjects/doses reporting each individual solicited local (any grade, Grade 3) and general (any grade, Grade 3, any causally related to vaccination and any Grade 3 causally related to vaccination) AE during the 7-days (Day 0 to Day 6) follow-up period will be tabulated for each group as follows:

- Overall, the percentage of subjects with the symptom and its exact 95% CI.
- Overall, the percentage of doses with the symptom and its exact 95% CI.
- At each study dose (visit), the percentage of subjects with the symptom and its exact 95% CI.

Statistical Analysis Plan

Study alias & e-track number(s): NTHI MCAT-001 (201281)

The exact 95% CIs will be calculated assuming independence between doses. For fever, additional analyses will be performed by 0.5°C increments.

The verbatim reports of **unsolicited symptoms** will be reviewed by a physician and the signs and symptoms will be coded according to the MedDRA Dictionary for Adverse Reaction Terminology. Every verbatim term will be matched with the appropriate preferred term (PT). The percentage of subjects with unsolicited symptoms within 30 days after any doses with its exact 95% CI will be tabulated by group and by MedDRA PT. Similar tabulation will be done for Grade 3 unsolicited symptoms, for unsolicited symptoms that resulted in a medically attended visit, for unsolicited symptoms causally related to vaccination and for Grade 3 symptoms causally related to the vaccination.

For each group and for each **haematology and biochemistry parameter**:

- The percentage of subjects having haematology and biochemistry results below or above the normal laboratory ranges will be tabulated by time point.

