- The maximum grading from Screening up to Visit 6 (Day 90) will be tabulated (grades will be based on local laboratory normal ranges and derived from FDA Guidance to Industry “Toxicity Grading Scale for Healthy Adult and Adolescent Volunteers Enrolled in Preventive Vaccine Clinical Trials”. Those laboratory parameters not included in the FDA grading scale will not be graded).

The number of subjects who experienced at least one SAE or any pIMDs from first vaccination up to 30 days post-Dose 2 will be reported.

The percentage of subjects/dose using **concomitant medication/ product** (any medication/ product, any antipyretic and any antipyretic taken prophylactically, respectively) during the 30-day follow-up period (Day 0 – Day 29) will be summarised per group for each dose and overall per dose.

The number of subjects who experienced any **AE leading to study withdrawal, or any SAE related to study participation or concurrent GSK medication/ vaccination**, from first vaccination up to 30 days post-Dose 2 will be reported.

Pregnancy reports from first vaccination up to 30 days post-Dose 2 and pregnancy outcomes will be described in detail.

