- The maximum grading from Screening up to Visit 8 (Day 420) will be tabulated (grades will be based on local laboratory normal ranges and derived from FDA Guidance to Industry “Toxicity Grading Scale for Healthy Adult and Adolescent Volunteers Enrolled in Preventive Vaccine Clinical Trials”. Those laboratory parameters not included in the FDA grading scale will not be graded).

The number of subjects who experienced at least one SAE or any pIMDs from first vaccination up to study conclusion will be reported.

The percentage of subjects/dose using **concomitant medication/ product** (any medication/ product, any antipyretic and any antipyretic taken prophylactically,

Study alias & e-track number(s): NTHI MCAT-001 (201281)

respectively) during the 30-day follow-up period (Day 0 – Day 29) will be summarised per group for each dose and overall per dose.

The number of subjects who experienced any AE leading to study withdrawal, or any SAE related to study participation or concurrent GSK medication/ vaccination, from first vaccination up to study conclusion will be reported.

Pregnancy reports from first vaccination up to study conclusion and pregnancy outcomes will be described in detail.

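### The graded laboratory table takes its maximum from Screening onwards, so a grade seen only before Dose 1 can be shown as a subject's worst grade

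*SAP*

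**What the plan says.** SAP 5.1 (Amendment 2) gives the laboratory part of the primary endpoint as "Occurrence of haematological and biochemical laboratory abnormalities, after vaccination, in all subjects, in all vaccine groups", and lists Day 7, 60, 67, 210 and 420.

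Two laboratory summaries are described for each analysis:

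- An ungraded one: the percentage of subjects with "results below or above the normal laboratory ranges will be tabulated by time point" (SAP 7.1.2, and the same in 7.2.2).
- A graded one, using the FDA toxicity scale. SAP 7.1.2: "The maximum grading from Screening up to Visit 6 (Day 90) will be tabulated". SAP 7.2.2: "The maximum grading from Screening up to Visit 8 (Day 420) will be tabulated". Protocol 10.6.2 has the same rule to Day 420.

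Blood for safety is drawn at Screening and on Day 0 as well as after vaccination (Protocol 3.1). Table 13 in Protocol 5.7.4.2 labels the Day 0 sample as pre-vaccination: "Visit 1 (Day 0) | Pre-Vacc I".

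On who may enter, Protocol 4.3.1 excludes Step 1 subjects with clinically significant "abnormalities as per the opinion of the investigator". For Step 2, Protocol 4.3.2 notes that "various pre-existing laboratory abnormalities might be detected" and leaves clinical significance to the investigator. Neither criterion sets a grade limit. Protocol 5.6.14.1 lets subjects with borderline Screening results go on to Visit 1 after a re-test.

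**The concern.** The graded table is the only summary in the protocol and SAP text that shows how severe laboratory abnormalities were. A reader will take it as describing the period after vaccination, because that is the period the endpoint names. In the same SAP sections, SAEs and pIMDs are counted from first vaccination. The laboratory maximum instead begins before any vaccine is given.

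A subject whose worst value was at Screening or on Day 0 is then displayed at that grade, and nothing in the described table marks it as pre-existing. The text provides no cross-tabulation by baseline grade, no grade by visit, and no restriction to grades that arose after Dose 1. At stake is how well the display of laboratory severity can be read in a Phase I study whose primary objective is safety.

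**Working it through.** The plan gives no baseline laboratory rates and no figure for this table, so there is nothing of its own to reproduce. The check has three steps.

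**1. What the window contains.** Scheduled safety samples, from Protocol 3.1 and Table 13 (none is scheduled at Visit 6 itself):

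| Analysis | Before Dose 1 | After Dose 1 | Share before Dose 1 |
|---|---|---|---|
| To Visit 6 (Day 90) | Screening, Day 0 | Day 7, 60, 67 | 2 of 5 (40%) |
| To Visit 8 (Day 420) | Screening, Day 0 | Day 7, 60, 67, 210, 420 | 2 of 7 (29%) |

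The samples after Dose 1 are exactly the endpoint's days. The two before it are not among them. Re-tests of borderline Screening results would be further samples before Dose 1.

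**2. What the rule does to one subject, for one parameter.**

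| Highest grade before Dose 1 | Highest grade after Dose 1 | Shown by the stated rule | Maximum after Dose 1 only |
|---|---|---|---|
| 0 | 1 | 1 | 1 |
| 1 | 0 | **1** | 0 |
| 1 | 1 | 1 | 1 |
| 1 | 2 | 2 | 2 |
| 2 | 1 | **2** | 1 |

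The two columns differ only where the earlier grade resolved or improved. Entry at a low grade is plausible: in Table 26 (Protocol Appendix C), Grade 1 ALT or AST begins at 1.1 times the upper limit of normal, which an investigator may well judge not clinically significant.

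**3. Size.** Fix one parameter and one grade, counted as that grade or higher. Let b be the share of a group with it before Dose 1, r the share of those without it at every later sample, and q the share of the remaining subjects who first reach it after Dose 1.

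- Shown by the stated rule: b + (1 − b)q
- After Dose 1 only: b(1 − r) + (1 − b)q
- Difference: b × r

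Both b and r are assumptions:

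| b | r = 0 | r = 0.25 | r = 0.5 | Subjects in a group of 30 at r = 0.5 |
|---|---|---|---|---|
| 2% | 0 | 0.5 points | 1.0 points | 30 × 0.010 = 0.3 |
| 5% | 0 | 1.25 points | 2.5 points | 30 × 0.025 = 0.75 |
| 10% | 0 | 2.5 points | 5.0 points | 30 × 0.050 = 1.5 |

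Between groups with the same b, the displayed difference changes by b times the difference in r. It is unchanged if earlier grades clear equally often in both groups. It shrinks if they clear less often in the vaccine group.

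**The case against.** The strongest reply is that the endpoint is already served. SAP 5.1 asks for any abnormality on stated days, without a grade and without requiring that it be new, and the by-time-point table reports exactly that. A reader might infer that the primary laboratory endpoint is misreported. The documents do not support that inference, because the table by time point does not use this window.

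The reply continues:

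- Clinically significant findings, and those that worsen from baseline, become AEs (Protocol 8.1.4) and receive an intensity grade (8.3.3.2.1).
- Holding rule 2c has its own 7-day post-vaccination window (Table 22).
- Clinically significant Screening abnormalities are excluded, so high grades before Dose 1 should be uncommon.
- The analysis is descriptive, and the SAP agrees with the protocol, so there is no deviation.
- Individual listings come with the final analysis (SAP 9.1).
- Table shells are in a separate annex that was not available for this review and may hold a shift table.

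All of this limits the effect, and none of it changes the stated window. The by-time-point table carries no grade. The AE route covers only findings judged clinically significant, graded by clinical judgement and not on the laboratory scale. Rule 2c is a monitoring rule limited to Grade 3. The content of the listings is not stated. If the annex already shows grade against baseline, the SAP sentence should say so.

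A reader might also infer that the table hides severity arising after vaccination. It does not: a maximum always shows a higher later grade.

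**Conclusion.** The point holds as a small fault in one descriptive table. By the rule as written, a grade present only before Dose 1 is displayed as the subject's worst grade, and improvement or resolution is hidden. Rates of post-vaccination severity read from that table can be too high by b × r. This is nothing if grades persist, and 0.5 to 5 points over the assumed ranges above. The documents do not show where in that range the study would fall. No test or decision rule is attached to the table.

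Two larger readings should be set aside. First, treating all samples as independent, with a 5% chance of a grade at each, gives 1 − 0.95^5 = 22.6% shown at Day 90 against 1 − 0.95^3 = 14.3% after Dose 1 only. More than a third of the graded subjects would then owe their entry to earlier samples. That calculation requires 0.95^3 = 86% of subjects graded before Dose 1 to be free of the grade at every later sample to Day 90, and nothing in the documents supports so little persistence.

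Second, the haemoglobin rows in Table 26 that grade change from baseline, where even the smallest fall is Grade 1, might suggest that many subjects are graded before vaccination. The documents say neither that those rows will be used nor which value is the baseline, and SAP 7.1.2 bases grades on laboratory normal ranges. If the rows were used, most of the resulting Grade 1 entries would come from the row itself and not from the window.

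**What to change.** In SAP 7.1.2 and 7.2.2, define the graded table as the maximum grade over samples after Dose 1: Day 7, 60 and 67 for the Day 90 analysis, plus Day 210 and 420 for the final one. Cross-tabulate it, per parameter and group, by the last grade before Dose 1 (Day 0, or the latest earlier sample if Day 0 is missing). If the haemoglobin change rows are to be used, state that the same last pre-Dose 1 value is the baseline.

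Align Protocol 10.6.2 at the next amendment. Alternatively, describe and justify the change in the study report, as Protocol 10.8 provides; an amendment for this alone is not needed.

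The cost is a sentence in each of two SAP sections and one revised table shell. No new data are required.

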7.1.3. Analysis of immunogenicity

The primary analysis will be performed on the ATP cohort for immunogenicity and if, in any study group, the percentage of vaccinated subjects with serological results excluded from the ATP cohort is at least 10%, a second analysis will be performed on the TVC.

Study alias & e-track number(s): NTHI MCAT-001 (201281)

7.1.3.1. Humoral immune response

Within group evaluation

For each group, at each time point during which blood samples are collected for humoral immune response and for each assay:

- Seropositivity rate and their exact 95% CI will be tabulated.
- GMCs and their 95% CI will be calculated.
- Antibody concentrations distribution will be investigated using Reverse Cumulative Curves.

These analyses will also be performed for each level of the following minimisation factors: age (50-59 years vs. 60-70 years), smoking status (current vs. former smoker), FEV₁/FCV ratio (≥ 0.7 vs. < 0.7).

Between groups evaluation (only for Step 2)

Comparative analyses will be exploratory with the aim to characterise the difference between the 10-10-10-AS and 10-10-3-AS groups in humoral immune response.

The difference in terms of GMCs will be evaluated, one month post-Dose 2, by computing the 95% CIs of the GMC ratio between groups for Step 2 by using a one-way ANCOVA model on the logarithm10 transformation of the concentrations/ titres. The ANCOVA model will include the group category, the age category, the smoking status and FEV₁/FVC (≥ 0.7 or < 0.7) and the pre-Dose 1 concentration (as covariate) as fixed effects. The groups will be considered significantly different if the 95% CI for the GMC ratio between the two groups does not contain the value 1.

However, these differences should be interpreted with caution considering that there will be no adjustment for multiplicity of endpoints.

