The lungs are known to be colonised with different strains of bacteria [Erb-Downward, 2011]. In COPD patients, acquisition of new bacterial strains is believed to be an important cause of AECOPD [Sethi, 2002]. Although estimates vary widely, non-typeable *Haemophilus influenzae* (NTHi) appears to be the main bacterial pathogen associated with AECOPD (11-38%), followed by *Moraxella catarrhalis* (Mcat) (3-25%) and *Streptococcus pneumoniae* (4-9%) [Alamoudi, 2007; Bandi, 2003; Hutchinson, 2007; Ko, 2007; Larsen, 2009; Murphy, 2005; Papi, 2006; Rosell, 2005; Sethi, 2002; Sethi, 2008; Wilkinson, 2006].

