1.2.3. Rationale for the use of placebo

The placebo group (saline solution) is included in the NTHI MCAT-001 study as a control for both safety and immunogenicity assessments.

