4.2. Secondary objective

- To evaluate the humoral and cellular immune response of the NTHI-Mcat investigational vaccines.

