7.2.3.1. Humoral immune response

Within group evaluation

For each group, at each time point during which blood samples are collected for humoral immune response and for each assay:

- Seropositivity rate and their exact 95% CI will be tabulated.
- GMCs and their 95% CI will be calculated.
- Antibody concentrations distribution will be investigated using Reverse Cumulative Curves.

These analyses will also be performed for each level of the following minimisation factors: age (50-59 years vs. 60-70 years), smoking status (current vs. former smoker), FEV₁/FCV ratio (≥ 0.7 vs. < 0.7).

Between groups evaluation (only for Step 2)

Comparative analyses will be exploratory with the aim to characterise the difference between the 10-10-10-AS and 10-10-3-AS groups in humoral immune response.

The difference in terms of GMCs will be evaluated, one month post-Dose 2, by computing the 95% CIs of the GMC ratio between groups for Step 2 by using a one-way ANCOVA model on the logarithm10 transformation of the concentrations/ titres. The ANCOVA model will include the group category, the age category, the smoking status and FEV₁/FVC (≥ 0.7 or < 0.7) and the pre-Dose 1 concentration (as co-variable) as fixed effects. The groups will be considered significantly different if the 95% CI for the GMC ratio between the two groups does not contain the value 1.

Study alias & e-track number(s): NTHI MCAT-001 (201281)

However, these differences should be interpreted with caution considering that there will be no adjustment for multiplicity of endpoints.

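### Placebo is included as an immunogenicity control, but the plan specifies no vaccine-versus-placebo humoral contrast and presents the two placebo groups pooled

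*SAP*

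**What the plan says.** **Role of placebo.** Protocol 1.2.3: "The placebo group (saline solution) is included in the NTHI MCAT-001 study as a control for both safety and immunogenicity assessments". About 15 subjects (PLACE1) and 30 subjects (PLACE2) receive it, 45 of about 120.

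**Objective.** SAP 4.2: "To evaluate the humoral and cellular immune response of the NTHI-Mcat investigational vaccines". No hypothesis or comparator is stated.

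**Within-group outputs.** SAP 7.1.3.1 and 7.2.3.1 give seropositivity with exact intervals, GMCs with 95% intervals and reverse cumulative curves. These cover every group, visit and assay, so placebo is included. They are repeated by age band, smoking status and FEV1/FVC category.

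**Between-group output.** This is limited to Step 2. SAP 7.1.3.1: "Comparative analyses will be exploratory with the aim to characterise the difference between the 10-10-10-AS and 10-10-3-AS groups in humoral immune response". The method is "computing the 95% CIs of the GMC ratio between groups for Step 2 by using a one-way ANCOVA model", and groups count as different "if the 95% CI for the GMC ratio between the two groups does not contain the value 1". Protocol 10.6.3.1 says the same. Section 7.2.3.1, which covers follow-up to Day 420, still places this evaluation at one month post-Dose 2.

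**Placebo display.** The SAP's group table gives PLACE1 and PLACE2 separate labels and also a common pooled label. SAP 7.1 and 7.2 say results are presented with the two placebo groups pooled across steps. Protocol 10.6 speaks only of presentation by study group, and SAP section 10 records no change from planned analyses.

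**The concern.** The subjects declared to be the immunogenicity control never enter an estimated humoral contrast. Between-group evaluation is confined to Step 2, so 10-10-10 has no comparison with PLACE1. In Step 2 the named aim covers only the adjuvanted pair, so neither formulation has an estimated ratio to PLACE2. At Day 210 and Day 420, both secondary-endpoint visits, there is no between-group estimate of any kind.

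The other planned outputs do not supply one. Seropositivity means being at or above the assay cut-off, which antibody present before vaccination can satisfy. The summary score is centred on the active groups' own average, so it carries no information about placebo.

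At stake is a randomised estimate, with an interval, of how far antibody levels under each formulation exceed those under placebo. It could matter most at the persistence visits if levels have fallen by then and the separation is no longer obvious by eye.

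**Working it through.** **The plan's own figures.** The sample-size section concerns adverse events only. Its 78.5% chance of seeing an event with 5% incidence among 30 subjects reproduces: 1 − 0.95^30 = 0.785. It does not bear on this point. No SD, effect size or precision is given for any humoral comparison, so every magnitude below rests on assumptions.

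**1. What is specified.**

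| Contrast | Day 90 | Day 210 | Day 420 |
|---|---|---|---|
| 10-10-10-AS / 10-10-3-AS | ANCOVA ratio | none | none |
| 10-10-10-AS / PLACE2 | none named | none | none |
| 10-10-3-AS / PLACE2 | none named | none | none |
| 10-10-10 / PLACE1 | none | none | none |

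**2. Effect of pooling.** The pool has 15 Step 1 and 30 Step 2 subjects. On the log scale its mean is one third PLACE1 and two thirds PLACE2. If the two placebo GMCs differ by a factor f (assumed), the pooled GMC differs from PLACE2 by f^(15/45) and from PLACE1 by f^(30/45).

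| f (assumed) | Step 2 reading off by | Step 1 reading off by |
|---|---|---|
| 1.25 | 1.08 | 1.16 |
| 1.5 | 1.14 | 1.31 |
| 2 | 1.26 | 1.59 |

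**3. Precision of an own-step ratio.** Assumed log10 SD: 0.3, 0.4 and 0.5. All intervals are two-sided 95%; entries are the multiply-or-divide factor around the ratio.

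- Unadjusted, n per group: 10^[t(2n−2) × SD × √(2/n)].
- Covariate-adjusted, Step 2 pair of 30 and 30, baseline correlation r assumed 0.5 to 0.7: 10^[t(54) × SD × √(1−r²) × √(2/30)]. The 54 degrees of freedom are 60 subjects less six parameters (intercept, group, three binary factors, baseline). Example, SD 0.3 and r = 0.7: 2.005 × 0.3 × 0.714 × 0.258 = 0.111, and 10^0.111 = 1.29.

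| | SD 0.3 | SD 0.4 | SD 0.5 |
|---|---|---|---|
| Step 2, unadjusted, 30 v 30 | 1.43 | 1.61 | 1.81 |
| Step 2, unadjusted, 27 v 27 (10% loss) | 1.46 | 1.65 | 1.88 |
| Step 2, adjusted, 30 v 30 | 1.29–1.36 | 1.41–1.51 | 1.53–1.68 |
| Step 1, unadjusted, 15 v 15 | 1.68 | 1.99 | 2.37 |

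**4. Side-by-side reading.** A reader who has only separate group intervals may look for non-overlap. With 30 per group and equal SDs this needs a ratio of 10^[2 × t(29) × SD/√30] = 1.68, 1.99 or 2.36. A direct ratio excludes 1 at the smaller factors in step 3. The fair like-for-like gain is 1.68–2.36 against the unadjusted 1.43–1.81. The further step to 1.29–1.68 comes from covariate adjustment. The plan does not propose non-overlap as a rule; it is only what an informal reader tends to do.

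**The case against.** The strongest reply is that this is a descriptive Phase I study with a safety primary objective. Protocol 10.7 says neither power nor type I error is controlled, and the secondary objective is only to evaluate the response. Calling placebo a control does not promise an inferential contrast, and the planned comparison serves formulation choice. All of that stands. It makes the gap one of specification, and it is why any added ratio should remain exploratory.

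A reader might infer that the humoral objective rests only on uncontrolled levels, or that a vaccine effect cannot be separated from existing antibody or natural boosting. The documents do not support either reading. Concurrent randomised placebo subjects get the same GMCs, seropositivity rates and curves at every visit, including Day 0, so drift would be visible. The subgroup tables by age band show PLACE2 without PLACE1, because Step 1 subjects are too young to enter them. What survives is narrower: those tables split PLACE2, Step 1 has no equivalent, and the overall display is stated to be pooled. The table templates in the annex may show the groups separately, but the SAP text does not say so.

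The wording about a ratio between groups for Step 2 could be read to include PLACE2. The stated aim and the two-group decision rule point the other way, and one sentence would settle it.

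It is also tempting to treat natural boosting and waning as facts. Protocol 1.1.1 says: "The lungs are known to be colonised with different strains of bacteria". Its statement on acquiring new strains, however, concerns COPD patients, and Step 2 excludes diagnosed COPD while allowing mild obstruction. The documents contain no persistence data. Both are possibilities only.

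Finally, one ANCOVA over all three Step 2 groups would impose a common baseline slope and residual variance. That could shift the estimate for the adjuvanted pair, on which SAP 7.2.3.3 leans to confirm the selected group. This objection is sound, and the fix avoids it.

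**Conclusion.** The point holds as a gap in specification. Placebo is the declared immunogenicity control, no vaccine/placebo humoral ratio is specified for either step or any visit, and the stated pooling means the main display is not a within-step comparison. It does not invalidate the humoral objective, because placebo levels with intervals are reported and an informal reading remains possible.

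In size, pooling distorts that informal reading by 1.08 to 1.26-fold in Step 2 and 1.16 to 1.59-fold in Step 1, if the placebo GMCs differ by 1.25 to 2-fold. A direct Step 2 ratio would carry a 95% factor of 1.43 to 1.81 unadjusted, or 1.29 to 1.68 with the planned covariates. In Step 1 it would be 1.68 to 2.37 unadjusted. These figures depend on the assumed log10 SD of 0.3 to 0.5, the baseline correlation of 0.5 to 0.7 and the placebo differences. Large Day 90 responses may be plain without any contrast; the gain there would be an estimate with an interval.

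**What to change.** In SAP 7.1.3.1 and 7.2.3.1, with protocol 10.6.3.1 aligned:

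- Show PLACE1 and PLACE2 separately for all humoral results.
- Leave the planned ANCOVA of 10-10-10-AS against 10-10-3-AS unchanged, and state that it uses those two groups only.
- For each antigen, add exploratory adjusted GMC ratios with 95% intervals for 10-10-10-AS/PLACE2 and 10-10-3-AS/PLACE2 at Day 90, Day 210 and Day 420. Use the same covariates in separate pairwise models, so that the estimate for the adjuvanted pair cannot move.
- Add a 10-10-10/PLACE1 ratio adjusted for pre-Dose 1 concentration.

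The cost is SAP wording, programming and tables, with no new subjects, visits or samples. Four antigens × two contrasts × three visits adds 24 Step 2 intervals, against four ratios (one per antigen) now planned. Step 1 adds four per visit, or 12 if reported at the same three visits. All are exploratory and unadjusted for multiplicity, which the SAP's existing caution should be extended to cover. Each pairwise model still assumes a common baseline slope and residual variance within its pair, so that should be checked when the ratios are reported.
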